EMA Assessment Period: The current study will employ a 1-week baseline EMA period followed by a 2-week experimental EMA protocol that uses a combination of event- and signal-contingent assessments. Based on previous EMA research, participants will be instructed to initiate a morning assessment each day to assess behaviors that may not have been captured during the in-vivo assessments the previous evening (*“How many alcohol drinks did you consume yesterday?; How many alcohol drinks do you plan to consume today?”*)¹⁰. They will be provided with examples of standard drinks to help accurately assess their drinking. In addition, participants will complete the imagery subscale from the Craving Experience Questionnaire (CEQ)¹¹ to retrospectively measure their strongest episode of craving during the previous day. Participants will also be prompted once per day to complete a Cue Reactivity Ecological Momentary Assessment (CREMA). CREMA provides real-time responses to alcohol-related stimuli presented in participant’s natural environment. Participants will be randomly prompted between 2:00-9:00 PM to begin a CREMA session. Participants will have 60 minutes to respond to the prompt. Participants will complete baseline measure of craving, stress and mood, and then view a photograph of an alcoholic beverage. Each item will be presented for 30 seconds. Different photographs will be presented at each study trial. After viewing the photograph, participants will be complete post ratings of their craving, stress and mood.

Between the hours of 2:00 p.m. and 9:00 p.m., participants will receive up to three random text message prompts to complete in-vivo assessments assessing craving and mood including: “How many standard drinks have you consumed since your last assessment?; “Are you drinking alcohol right now?; “How is your mood right now?; “How stressed do you feel right now.” “How strong is your craving for alcohol right now...” An automated text message system will be used with at least 1-hour between assessments and will de-activate after an hour has expired. Participants who responded to at least 80% of the morning assessments will be invited to continue participation in the experimental portion of the study.

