During, the experimental phase, the same assessments will be administered. In addition, any occasion in which a positive response to current craving is reported, an automated prompt will be displayed to re-rate cravings four minutes later. Participants in the experimental condition will receive an automated prompted to complete the Tetris task in-between the ratings. After four minutes the application will upload a screen shot of the Tetris game into RedCAP. The Tetris task involves manipulating basic shapes to form rows that then disappear. Participants in the experimental condition will be asked to play Tetris after CREMA sessions and after any of the three random craving assessment that participants report experiencing craving. Participants in the control condition will just be asked to re-rate craving four minutes later and report what activities they completed during the three-minute break.

Post-Experiment Assessment: Participants will complete self-report questionnaires via REDCap. In addition, participants will complete the TLFB over a video call at a 1-month follow-up. Figure 1 below illustrates the study design.

Figure 1. Study design

Statistical Analyses

To establish feasibility, descriptive analyses will be used to measure the proportion of prompts participants respond to, and the response time to complete prompts. An intent-to-treat analysis will be conducted with mixed-effects regression to test between-group differences in urge to drink after completing the task, nested within individuals. We will use a random-effects mixed modeling approach using maximum likelihood estimation to test differences in mean craving and drinking outcomes (i.e., alcohol consumption) between baseline and post-experiment. We will test differences in alcohol consumption between baseline and one-month follow-up. Participants will be modeled as random factors and the group allocation will be a fixed factor. Maximum likelihood estimation will provide unbiased estimates assuming missingness at random.¹³

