Descriptive analyses will be used to describe the sample. Clinical outcomes of interest are defined as: (1) decrease in craving measured by a single item from the Visual Analogue Scale immediately after task completion and from baseline to 2-week intervention phase (2) decrease in number of standard drinks (amount) from baseline to 2-week intervention phase and at 1-month follow-up measured by daily reports of “how many standard drinks did you consume yesterday?”. In order to establish feasibility, descriptive analyses will be used to measure the proportion of prompts participants responded to and response time to complete prompts. Intent to treat mixed-effects regression will be conducted to test differences in craving items after completing the task, nested within individuals. We will use a random effects mixed modeling approach using maximum likelihood estimation to test differences in mean craving and drinking outcomes (i.e., alcohol consumption) between baseline and post-experiment. We will also test differences in alcohol consumption between baseline and one-month follow-up. The participants will be modeled as random factors and the group allocation will be a fixed factor. We will examine the intervention between intervention and study time (baseline versus follow-up). Maximum likelihood estimation will provide unbiased estimates assuming missingness at random. [name] will be attending a summer statistical workshop in ecological momentary assessment data analysis and receive consultation from statisticians housed within the South Carolina Clinical & Translational Research Institute to support the proposed analyses in this project.

STUDY TIMELINE

| Overview of Study Timeline | | Months | | | | |
|-------------------------------------|--|--------|---|------|----|-----|
| | | 1 | 2 | 3-11 | 12 | 13+ |
| Tasks/Activities | | | | | | |
| Study Start Up | | ↔ | | | | |
| Recruitment | | | ↔ | → | | |
| Conduct Randomized Controlled Trial | | ↔ | → | | | |
| Data Cleaning/Analysis | | | ↔ | → | | |
| Dissemination | | ↔ | → | | | |

References

- ¹Substance Abuse and Mental Health Services Administration (SAMHSA). National Survey on Drug Use and Health (NSDUH). 2015 (NSDUH-2015-DS0001) Public-Use File Dataset. Available at: <https://www.datafiles.samhsa.gov/study-dataset/national-survey-drug-use-and-health-2015-nsduh-2015-ds0001-nid16894>.

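### The immediate-craving model leaves out the craving rating taken four minutes earlier and the stratification scores; run as written, it compares post-task craving only.

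*Combined protocol and SAP*

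**What the plan says.** The Statistical Design and Power section defines the immediate outcome as a "decrease in craving measured by a single item from the Visual Analogue Scale immediately after task completion". The model sentence in that section is: "Intent to treat mixed-effects regression will be conducted to test differences in craving items after completing the task, nested within individuals". The Statistical Analyses section of the Approach says the same in other words: mixed-effects regression "to test between-group differences in urge to drink after completing the task, nested within individuals". On terms, the plan says: "The participants will be modeled as random factors and the group allocation will be a fixed factor". The only time factor named is baseline versus follow-up. It belongs to the comparison of study phases, not to the two ratings within one occasion.

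The experimental-phase procedures supply the second rating. On "any occasion in which a positive response to current craving is reported, an automated prompt will be displayed to re-rate cravings four minutes later". Controls re-rate at the same point, so a before-and-after pair exists in both arms.

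Cue-reactivity (CREMA) sessions hold two ratings before any Tetris. First: "Participants will complete baseline measure of craving, stress and mood, and then view a photograph of an alcoholic beverage". Then: "After viewing the photograph, participants will be complete post ratings of their craving, stress and mood". The plan does not say which of the two is the reference.

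The Baseline Visit paragraph stratifies randomisation by self-reported craving and depression scores. Neither score appears in a stated model.

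**The concern.** The outcome definition and the model sentences do not match. A decrease needs a starting value. The model sentences contain only the value after the interval, and the Aim 1 hypothesis is worded as a lower level. A post-only model, a change score and a model adjusted for the pre-task rating could each be defended from the text, and they can give different answers. If none is fixed in advance, the choice falls after the data are seen.

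Two things are at stake. The first is precision: with 32 expected completers, a post-only analysis discards a rating that the trial already collects. The second is interpretation. Re-ratings are triggered by craving reported after randomisation, so the number of occasions and their starting level may differ between arms. If Tetris also affects craving in general, which is the second hypothesis of Aim 1, a post-only comparison mixes that with the immediate effect.

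**Working it through.** **The plan's own figures.** The power paragraph gives d = .50, alpha .05, power .80 and a total of 24. A two-sided two-sample t-test with these inputs needs 64 per arm, and 12 per group gives power .22. A repeated-measures group-by-time F-test with f = .25, four measurements and correlation .5 does give 24 (power .816), but the plan states neither the number of measurements nor the correlation. That is a separate matter and nothing below depends on it. The recruitment figure reproduces: 32/0.8 = 40.

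**Inputs.** From the plan: 32 completers allocated 1:1, so 16 per arm; d = .50; alpha .05. Assumed: two-sided test, one summary pair per woman, equal SDs before and after, d on the scale of the post-task SD, and pre/post correlation r from .3 to .8. The plan gives no correlation.

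**Formulas.** Power is from the noncentral t, with noncentrality d_eff × √(16/2) = 2.828 × d_eff.
- Post-only: d_eff = .50, noncentrality 1.414, 30 df.
- Change score: d_eff = .50/√(2(1 − r)), 30 df.
- Pre-task rating as covariate: d_eff = .50/√(1 − r²), 29 df.

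| r | Post-only | Change: d_eff, power | Covariate: d_eff, power |
|---|---|---|---|
| .3 | .278 | .423, .212 | .524, .300 |
| .5 | .278 | .500, .278 | .577, .352 |
| .7 | .278 | .645, .424 | .700, .482 |
| .8 | .278 | .791, .581 | .833, .625 |

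Adjustment beats post-only at every correlation tried. The change score loses to post-only below r = .5.

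**Stratification scores.** These were simulated with 40 women, assumed 2×2 strata, blocks of 4 and 20% dropout. With the pre-task rating already in the model, adding the strata moved power from .339 to .359 and from .602 to .604 (strata explaining 20% of variance, r = .5 and .8), and from .328 to .402 and from .613 to .626 (40%). The gain is 0 to 7 points. The main reason to include them is to match the analysis to the randomisation.

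**Direction of bias.** This was simulated with no immediate effect and re-ratings only after positive craving. The difference is experimental minus control, in SD of momentary craving.
- General effect is a uniform downward shift: post-only difference −.10 to −.16, which favours Tetris.
- General effect removes mild episodes and leaves the stronger ones: post-only difference +.05 to +.15, against Tetris.

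These inputs are assumed too, and only the change of sign should be taken from the result. Adjustment for the pre-task rating helps to a degree that depends on mechanism. If a general shift persists in full over the four minutes, it leaves 24 to 72% of the post-only bias, against 6 to 26% for a change score. If the re-rating instead follows a regression on the pre-task rating, adjustment leaves none.

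**Which occasions count.** On Tetris, the procedures say: "Participants in the experimental condition will be asked to play Tetris after CREMA sessions and after any of the three random craving assessment", followed by a craving condition that can be read as covering only the random assessments or the CREMA sessions as well. The Human Subjects section ties the re-rating to reported craving throughout. A CREMA session without craving might therefore bring Tetris but no re-rating.

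**The case against.** The strongest reply is that a decrease already means a change, and that the obvious reference is the rating that triggered the re-rating. That may be the intention, and it is why the plan cannot be said to have chosen a post-only analysis. But the word does not put a term in the model or say which CREMA rating is meant.

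A second reply is that the change score should be primary, because it leaves less carry-over when a general shift persists. That holds under that one assumption. If mild episodes drop out instead, the remaining occasions start higher and tend to fall further, so a change score would favour Tetris. Carry-over therefore does not decide between the two. Precision favours adjustment, and the change score belongs beside it.

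A reader might infer that a post-only model must flatter Tetris. The documents do not support this: they do not say which episodes a general effect would change, and the sign reverses between two plausible mechanisms. Nor do they support calling the comparison invalid. Craving triggers the same four-minute re-rating in both arms, and intent to treat is stated in both analysis sections, which points towards counting occasions when Tetris was prompted but not played.

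It is also fair that this is a pilot, that statistical consultation is planned, that d = .50 is not tied to this endpoint, and that one value per woman ignores up to 56 afternoon and evening prompts. These points limit the absolute power figures. They do not supply the missing model, and the plan does state significance hypotheses.

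**Conclusion.** The point holds. The immediate-craving model is not specified to the level its outcome definition requires, and as written it omits a rating available in both arms as well as the stratification scores. At 16 per arm and d = .50, power is .28 post-only against .30 to .63 adjusted and .21 to .58 for a change score. These figures rest on assumed correlations of .3 to .8 and one value per woman, so the ordering is more dependable than the levels. Bias from a general effect of Tetris is possible in either direction and its size is unknown. Adjustment for the pre-task rating reduces it but may not remove it. This should be corrected before analysis; it is not a flaw in the design or in the data collected.

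**What to change.** State the primary model for immediate craving as the re-rating on arm, the same occasion's last craving rating before the four-minute interval (for CREMA, the rating after the photograph), prompt type (CREMA or random) and the two stratification scores, with participant random effects. Include every occasion that triggers a re-rating, in both arms, whether or not Tetris was played. Give the change score as a sensitivity analysis. Report the number of occasions and the pre-task ratings by arm. Say plainly that the pre-task rating is measured after randomisation, so adjusting for it may not remove all carry-over from a general effect.

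Reconcile the experimental-phase procedures with the Human Subjects section on whether the craving condition applies to CREMA sessions.

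The cost is a few sentences of analysis text and one procedural clarification; every variable is already collected. The downside is a few more model terms in a small sample, and adjustment for a covariate measured after randomisation.

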We will register our trial in ClinicalTrials.gov within the timeframe specified in the NIH Policy on the Dissemination of NIH-Funded Clinical Trial Information. We will submit results of the trial to ClinicalTrials.gov no later than 1 year after participants have completed the trial, including the 6-month follow-up assessments. We will include a statement in our Consent and Assent forms regarding ClinicalTrials.gov.

MUSC's Office of Research and Integrity & Assurance Responsibilities administers ClinicalTrials.gov accounts and monitors research community activity and responsibilities within ClinicalTrials.gov. PI [name] will be responsible for creating records on ClinicalTrials.gov.

STATISTICAL DESIGN AND POWER

In the proposed study, 40 eligible participants will be initially recruited, assuming an estimated 20% dropout rate, in order to obtain data on 32 treatment completers. A moderate effect size is expected in the current study. Previous research testing visual cognitive interference tasks reported a medium effect size for models estimating craving strength ($f^2 = 0.12$; $n = 31$).⁵⁻⁶ A power analysis was conducted using G*Power 3.1 to detect a medium-sized between groups effect ($d = .50$, $\alpha = .05$) with a power of .80, a total sample of 24 is needed (i.e., 12 participants per group). However, due to this developmental nature of this study and the objectives to demonstrate preliminary efficacy, the proposed sample size is larger. The proposed study will therefore enroll 40 participants to be randomized to treatment to estimate an 80% study retention rate with a 95% confidence interval of $\pm 13\%$.

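### Fitting the linear mixed models by maximum likelihood, with no small-sample correction, makes tests of between-woman contrasts slightly too liberal at 32 to 40 participants (true level about 5.6% to 6.7% for a nominal 5%)

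*Combined protocol and SAP*

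**What the plan says.** The estimation method appears twice. The Statistical Analyses section of the protocol says "We will use a random-effects mixed modeling approach using maximum likelihood estimation", and the Statistical Design and Power section repeats it as "We will use a random effects mixed modeling approach using maximum likelihood estimation". The structure is given as "The participants will be modeled as random factors and the group allocation will be a fixed factor". Change over time is covered by "We will examine the intervention between intervention and study time (baseline versus follow-up"), which I read as the group-by-time interaction. The only reason given for the estimator is "Maximum likelihood estimation will provide unbiased estimates assuming missingness at random".

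On numbers, the plan says "40 eligible participants will be initially recruited, assuming an estimated 20% dropout rate", leaving 32 completers. Allocation is 1:1, 20 per arm (Human Subjects Involvement, Characteristics, and Design).

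The documents do not mention REML, Kenward-Roger or Satterthwaite degrees of freedom, a t reference or any other small-sample adjustment. They do not say how tests and intervals will be formed. Alpha of .05 appears only in the power statement, without sidedness. The software is SPSS and Stata, with no procedure or option named. Beyond participant as a random factor, no random slope is described.

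**The concern.** Group is assigned per woman. When a contrast's error lies between women, the information about that error comes from 32 to 40 people, however many prompts each one answers. ML estimates the between-woman variance without allowing for the fixed effects fitted, so the estimate is too small on average. A normal reference would make this worse, because it ignores the uncertainty in the variance estimate.

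The contrasts exposed are the group difference in re-rated or mean craving, and the group difference in change in craving or drinking when change varies between women or each woman supplies one summary per period. The comparison of baseline with 1-month drinking could take the latter form.

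The error is in the favourable direction: p-values slightly too small and intervals slightly too narrow. The power section gives preliminary efficacy as an aim, and intervals from a pilot may inform the design of a later trial.

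The plan's stated reason does not address this. Missingness at random concerns the validity of the estimates when data are incomplete. It says nothing about the variance or the test level in a small sample, and REML is valid under the same assumption.

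**Working it through.** **Inputs from the documents.** N = 40 recruited, 20% dropout, 32 completing, 1:1 allocation, alpha .05. **Assumed:** a two-sided test, and two person-level fixed effects (intercept and group), since the plan lists no covariates.

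**The plan's own figure.** 32 / (1 − 0.20) = 40. Reproduced.

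**Variance shortfall, balanced between-woman contrast.** ML divides by N where the unbiased estimate divides by N − 2.
- N = 40: 38/40 = 0.950, so the variance is 5.0% low. √0.950 = 0.9747, so the standard error is 2.5% low.
- N = 32: 30/32 = 0.9375, so the variance is 6.25% low. √0.9375 = 0.9682, so the standard error is 3.2% low.

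**True level of a nominal 5% two-sided test.** Under no effect, the correctly scaled statistic follows t with N − 2 degrees of freedom. Each version of the test amounts to a cut-off c on that scale, and the true level is P(|t(N−2)| > c).

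| Test | Cut-off c | N = 40 | N = 32 |
|---|---|---|---|
| ML, Wald z | 1.96 × √((N−2)/N) | c = 1.910, 6.4% | c = 1.898, 6.7% |
| ML, likelihood ratio | √((N−2)(exp(3.841/N) − 1)) | c = 1.957, 5.8% | c = 1.956, 6.0% |
| ML, t(N−2) | t.975(N−2) × √((N−2)/N) | c = 1.973, 5.6% | c = 1.977, 5.7% |
| REML, z | 1.96 | 5.7% | 5.9% |
| REML, t(N−2) | t.975(N−2) | c = 2.024, 5.0% | c = 2.042, 5.0% |

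At N = 32, ML alone accounts for about 0.7 points (5.7% against 5.0%). The rest of the 1.7-point excess in the Wald z row needs a z reference.

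**Simulation with missing records.** Random-intercept model, 14 daily records, about 25% missing, intraclass correlation 0.2 and 0.5 (both the missing share and the correlations are assumed), 12,000 runs per setting, Monte Carlo standard error about 0.2 points.
- ML with Wald z: 6.7% to 6.9% at N = 32; 6.2% to 6.5% at N = 40.
- REML with t(N−2): 5.0% to 5.2% at N = 32; 4.7% to 5.2% at N = 40.

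**Group-by-time interaction on 7 baseline and 14 intervention days.**
- *Random intercept only, no true variation in change.* The error comes from the daily records. At N = 32, ML divides by 32 × 20 = 640 where 638 is correct, and P(|t(638)| > 1.96 × √(638/640)) = 5.1%. At N = 40 the corresponding figures are 800 and 798, again 5.1%. Simulation (5,000 runs, Monte Carlo standard error about 0.3 points) gave 5.6% and 5.2%. This is close to nominal.
- *Change analysed per woman* (equivalent, in the balanced case, to a random phase slope). The error lies between women again. Simulated ML Wald z gave 6.1% to 7.0% at N = 32 and 6.5% at N = 40, around the exact 6.7% and 6.4%.
- *Random intercept only, but change truly varies* (slope variance 0.1, assumed, against a residual variance of 0.6). The simulated level at N = 32 was 13%. That comes from the omitted slope and not from ML.

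**The case against.** The strongest objection is about scope. The plan names only participant as a random factor. Read literally, that is a random intercept, and in such a model the group-by-time interaction on daily records is a within-woman contrast on which ML has almost no effect. This stands. A reader might infer that all the hypothesised effects are inflated, but the documents do not support that. The inflation applies to between-woman contrasts, and it reaches the change analyses only if change varies between women or each woman contributes one summary per period.

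Second, the z reference is not in the plan. This also stands: the 6.4% to 6.7% figures are conditional on it. The direction does not depend on it, because every ML-based test in the table exceeds 5%.

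Third, larger figures are tempting. One could add covariates, since randomisation is stratified by craving and depression scores (Baseline Visit), but neither analysis section puts those scores in the model. One could also compute at 24 women, where ML with z gives 7.4%. In the documents, 24 is only the result of the power calculation ("with a power of .80, a total sample of 24 is needed"), and they give no number of women expected to contribute re-ratings. Neither figure should be quoted as the size of the problem.

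Fourth, the sentence on unbiased estimates under missingness at random is not itself an error. The fixed-effect point estimates are not biased by the choice of ML over REML.

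Fifth, drinks are counts, and the plan does not say that every model is linear. For a count model, ML is the usual estimator, and REML with Kenward-Roger degrees of freedom does not transfer directly. This limits the remedy.

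Finally, this is a pilot with statistical consultation planned. That bears on severity, but the stated method remains ML without a correction.

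**Conclusion.** The point holds for between-woman contrasts analysed with a linear mixed model. At the planned numbers the true level of a nominal 5% test is about 0.6 to 1.7 points too high, depending on a reference distribution that the plan leaves open.

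The exact figures rest on a balanced two-arm contrast, two person-level parameters and a two-sided test. The simulations with missing records agree with them under assumed intraclass correlations and missingness.

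Severity is minor. The excess would matter mainly for a p-value near .05 or for a confidence interval carried into a later trial's design. It is not a reason to doubt the estimated effects themselves.

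**What to change.** In both the Statistical Analyses and the Statistical Design and Power sections, for each outcome analysed with a linear mixed model:

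- Replace maximum likelihood with REML.
- Specify Kenward-Roger or Satterthwaite degrees of freedom, with t-based tests and confidence intervals. Both parts are needed: REML with a z test would still run at 5.7% to 5.9%.
- State the random-effects structure, including a random phase slope for change from baseline.
- Keep the missing-at-random statement, reworded to refer to REML.

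Say which model will be used for drinks. If it is a count model, this fix does not carry over directly, and the plan should state separately how small-sample inference will be handled.

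The cost is a few lines of text and options in the model command, with slightly wider intervals and slightly larger p-values. If the alternative were ML with z, the z-based interval would be about 6% narrower than the correct one at N = 40 (1.910/2.024 = 0.944) and 7% narrower at N = 32 (1.898/2.042 = 0.929).

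### The 1-month drinking test, as described, leaves out the 2-week drinking data, so its missing-at-random protection is weaker than it could be if loss to follow-up differs by arm

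*Combined protocol and SAP*

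**What the plan says.** The analysis paragraph of STATISTICAL DESIGN AND POWER sets out two drinking comparisons. The first concerns "drinking outcomes (i.e., alcohol consumption) between baseline and post-experiment". The second is introduced as an addition: "We will also test differences in alcohol consumption between baseline and one-month follow-up". The earlier Statistical Analyses section has the same pair: "We will test differences in alcohol consumption between baseline and one-month follow-up".

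The model terms are brief: "The participants will be modeled as random factors and the group allocation will be a fixed factor". Time enters through this sentence: "We will examine the intervention between intervention and study time (baseline versus follow-up"; the first noun is presumably meant to be interaction. No covariate, auxiliary variable, covariance structure, imputation or sensitivity analysis is named.

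The specific missing-data statement is: "Maximum likelihood estimation will provide unbiased estimates assuming missingness at random". The data and safety monitoring section adds only a general remark that missing data will be considered in the analysis.

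Drinking in the 2-week phase is collected. Under EMA Assessment Period, "participants will be instructed to initiate a morning assessment each day", which includes the number of drinks on the previous day, and the experimental phase repeats the same assessments. The plan expects 20% dropout.

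Two places disagree on the 1-month measure. Post-Experiment Assessment uses the TLFB by video call. STATISTICAL DESIGN AND POWER defines the drinking outcome, 1-month value included, by daily reports.

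**The concern.** Maximum likelihood removes bias only when missingness is random given the data inside the fitted likelihood. A baseline and 1-month model fills in a lost 1-month value, in effect, from baseline drinking and arm. A woman whose drinking rose during the 2-week phase and who then dropped out is treated as if that rise had never been seen. Such data are missing at random given everything the trial collects, but not given the model described.

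At stake is the 1-month group contrast, which is part of the Aim 2 hypothesis. With about one woman in five expected to be lost, a mechanism that differs between arms would move the contrast. The two arms have different tasks, since one plays Tetris and the other only re-rates craving and reports activities. Arm-specific loss is therefore conceivable, but the documents give no evidence that it will occur.

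**Working it through.** **The plan's own figure.** 32 completers / (1 - 0.20) = 40, as stated. Expected loss is therefore 8 of 40.

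**Assumed inputs.** The documents give no correlations and no dropout mechanism. Drinking is scaled to SD 1 at each time. Correlations are written r12 (baseline, 2-week), r23 (2-week, 1-month) and r13 (baseline, 1-month).

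**Why the 2-week value matters.** Regress 1-month drinking on both earlier values:
- weight on 2-week = (r23 - r12 × r13) / (1 - r12²)
- weight on baseline = (r13 - r12 × r23) / (1 - r12²)

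With r12 = 0.6, r23 = 0.7, r13 = 0.5, these are (0.7 - 0.30)/0.64 = 0.625 and (0.5 - 0.42)/0.64 = 0.125. If completers differ from all women by some amount in baseline-adjusted 2-week drinking, the two-time model's 1-month arm mean is wrong by 0.625 times that amount. The group contrast is wrong by the difference between arms.

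**Large-sample simulation.** True contrast -0.50 SD; 20% dropout in each arm; loss logistic in observed 2-week drinking, with the log-odds slope per SD shown as (control, Tetris). Estimated contrasts:

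| r12, r23, r13 | Slopes | Two-time | Three-time, random intercept | Three-time, unstructured |
|---|---|---|---|---|
| 0.6, 0.7, 0.5 | (1, 1) | -0.501 | -0.501 | -0.502 |
| 0.6, 0.7, 0.5 | (1, 0) | -0.429 | -0.482 | -0.499 |
| 0.6, 0.7, 0.5 | (0, 1) | -0.566 | -0.514 | -0.497 |
| 0.5, 0.7, 0.4 | (0, 1) | -0.589 | -0.534 | -0.503 |
| 0.5, 0.7, 0.4 | (1, -0.5) | -0.362 | -0.449 | -0.498 |
| 0.7, 0.8, 0.65 | (1, 0) | -0.442 | -0.486 | -0.502 |

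- Same slope and same dropout rate in both arms: the contrast is unbiased, although with slopes of 0.5 to 1 each arm's mean is 0.03 to 0.09 SD too low.
- Slopes that differ by arm: bias of about 0.06 to 0.14 SD, in either direction.
- The unstructured three-time model recovers the truth. A random intercept removes only part of the bias.

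**One dropout equation common to both arms**, 20% overall, slopes 0.5 to 2. The true effect itself makes the dropout rates differ (for example 25.2% against 14.8%). The two-time contrast is -0.495 to -0.438, a bias of 0.005 to 0.06 SD towards zero. The three-time unstructured contrast is within 0.003 of -0.50.

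**Small-sample simulation**, 20 per arm, no true effect, two-time against three-time:
- 30% against 10% dropout, same link in both arms: -0.081 against -0.005.
- 20% in each arm, link in Tetris only: -0.109 against -0.006.
- 30% against 10%, link in Tetris only, r23 = 0.8: -0.155 against 0.002.

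A further run with loss depending on 2-week drinking and differing by arm gave 0.07 to 0.18 SD with two times and about zero with three.

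**Size against noise.** At N = 40 the SD of the two-time estimate is 0.343, and of the three-time unstructured estimate 0.335. Bias over standard error is 0.07/0.34 = 0.21 to 0.18/0.34 = 0.53. By normal approximation, two-sided false positives are Φ(-1.96 + 0.21) + Φ(-1.96 - 0.21), about 5.5%, to Φ(-1.96 + 0.53) + Φ(-1.96 - 0.53), about 8.3%, instead of 5%.

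**Early loss.** If half of the dropouts also lack 2-week data, the three-time model keeps a bias of 0.03 to 0.04 SD. If all lack it, nothing is gained (0.08 to 0.10 SD remains).

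**Day of week (minor).** Assume 1.5 drinks on weekdays, 3.5 on weekend days, and 10% of weekday reports missed. The observed phase mean is:
- 20% of weekend reports missed: (5 × 0.9 × 1.5 + 2 × 0.8 × 3.5)/(4.5 + 1.6) = 12.35/6.1 = 2.02.
- 40% missed: (6.75 + 2 × 0.6 × 3.5)/(4.5 + 1.2) = 10.95/5.7 = 1.92.

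If only the Tetris arm moves to 40%, and only in the experimental phase, the contrast shifts by 1.92 - 2.02 = -0.10 drinks per day. A weekend term removes this. With equal missingness in both arms the contrast is essentially unbiased.

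**The case against.** The strongest reply is that the two-time model is a reading of the text. The plan defines drinking over the 2-week phase and at 1 month within one outcome, then lists the comparisons of interest. It does not say that each is fitted to separate data, so a joint model with two contrasts is not ruled out. This stands. Still, nothing specifies such a model, and the two-level time factor points the other way.

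The missing-data sentence is also conditional, so a reader who calls it false goes too far. What it lacks is a statement of which data the condition refers to.

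A reader might infer that the planned model will show a benefit that does not exist. The documents do not support that. Bias in the contrast needs dropout that differs by arm, which no section predicts. It can hide a benefit as easily as create one, and it is at most about half a standard error in a pilot.

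The remedy has limits too. Randomization is described under Baseline Visit, before the EMA week and its 80% response requirement, so some losses may come before any 2-week data exist.

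The day-of-week issue is weaker: phases of 7 and 14 days balance weekdays by design. A reader might extend it to clock time or prompt type, but no calculation supports those terms, and hour has no bearing on a morning report of the previous day's drinks.

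**Conclusion.** The point holds as a moderate, inexpensive improvement. As described, the 1-month test does not use the 2-week drinking data, so the missing-at-random assumption it needs is stronger than necessary. If loss depends on 2-week drinking and differs by arm, the contrast can be biased by roughly 0.07 to 0.18 SD in either direction, against a standard error of about 0.34 SD. With the same mechanism and equal dropout in both arms it is essentially unbiased. A three-time unstructured model removes the bias for women who gave 2-week data. All correlations, dropout slopes and arm differences are assumed; only the 20% dropout and the sample of 40 come from the plan.

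**What to change.** 1. Reconcile Post-Experiment Assessment (TLFB) with STATISTICAL DESIGN AND POWER (daily reports): state which instrument supplies 1-month drinking and which baseline it is compared with.
2. Replace the separate comparisons with one maximum likelihood longitudinal model for drinking: baseline, 2-week and 1-month values, group, time, group by time, and an unstructured covariance. Read both the 2-week and the 1-month group contrasts from it.
3. State that missingness at random is assumed conditional on arm and these three measurements. Report how many women were lost before giving 2-week data, since the model helps little for them.
4. As a minor addition, include day of week in the model for daily drinks.

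The cost is a few lines of wording and code before analysis, with no new data or visits. The downside is a few more covariance parameters at N = 40: an unstructured 3 × 3 matrix has 6, against 3 for two times. In the simulation the standard error did not rise (0.335 against 0.343).
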